### **Sample Size and Power**

The primary objective of this study is to examine and validate the differences in neuroimaging changes and network expressions across different time points during the ECT treatment. We will use repeated measure ANOVA to analyze each of the neuroimaging measures between different timepoints. Traditional power analysis in neuroimaging is challenging not only because of the inherent multiple comparisons in our studies, but also due to the fact that different voxels have different signal to noise ratio, thus effect sizes. One possible approach would be to estimate the

effect size. In order to do that, we have to estimate the distribution of the magnitude of signal change and the within subject and between subject variance. In a motor area the signal change can be well above 1%, but with cognitive or perception tests the signal is usually around 0.5-1%. According power analysis calculations with these parameter estimates it was shown that 80% power can be reached with  $N=20$  sample size.Indeed, targeting for 20 subjects in neuroimaging studies is a common practice.

**Future Studies:** MRI images and diagnostic information will be kept in an IRB-approved data repository (IRB # 06.04.089; P.I.: [name]). All study information will be kept private and identifiable information will only be released with participant permission. Participants in the current study may also be contacted about the possibility of participating in future studies.

Funding source: Brain and Behavior Research Foundation: NARSAD Young Investigator Grant

Funding source: NIMH Advanced Center for Interventions and Services Research.

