have examined regional changes in blood flow or glucose consumption before and after ECT. However, the results of these studies were sometimes contradictory and this type of methodology was not suited to detect possible changes in brain networks. In this last decade novel fMRI techniques have became available to measure and evaluate networks in the brain. Hence, in this pilot study, we will also collect longitudinal MRI data (once before ECT and twice after ECT) to gain novel insight into the effect of ECT at a deeper level.

In addition, we will also explore other parameters of ECT, such as seizure duration and morphology as well as hemodynamic and behavioral changes when using ketamine versus methohexitol for ECT.

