### 1. Study Overview

This is a prospective, random assignment, double blind, parallel group pilot study comparing the efficacy of bifrontal ECT performed with ketamine anesthesia to that performed with methohexitol anesthesia in patients with a major depressive episode. We intend over a 2 year period, to recruit 24 patients who are scheduled to receive an acute course of ECT. Patients who are able and willing to provide written informed consent will be randomly assigned on a 1:1 ratio to receive either a course of bifrontal ECT using ketamine or methohexitol anesthesia. Subjects will receive a standard acute course of ECT (3X/week) and depressive symptomatology will be monitored with the Hamilton Rating Scale for Depression (HRSD-24) before each treatment.

The primary outcome will be the number of treatments needed to achieve remission. Remission is defined as two consecutive HRSD scores  $\leq 10$ , and HRSD total score does not change  $> 3$

points or remains < 6 at the last two consecutive treatments. For the secondary aim of this pilot study we will monitor cognitive changes before and after each ECT treatment, and at the end of the treatment course. In addition, we will collect data on other treatment parameters such as seizure duration, electroencephalogram (EEG) morphology, hemodynamic changes, and emergence of any psychotic symptoms post treatment.

Parallel with these procedures we will also collect magnetic resonance imaging (MRI) data on these subjects. The timeline of neuroimaging and its relation to ECT is illustrated in Figure 1.

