## **9. Adverse Event Reporting**

Side-effects will be monitored by the study physician and self reports. Treatment side effects will be measured using the Treatment Emergent Side Effects Scale (TESS). Reported adverse events will be evaluated and treated according to standard treatments procedures. In the case of a serious or intolerable adverse event subjects will be withdrawn from the study and he will be referred for treatment if necessary. Serious adverse events will be reported to IRB in no more than 24 hours after occurrence or after the ECT psychiatrist is informed.

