### **Group analysis**

Our main goal in our analysis is to determine group-wise effects. The inter-subject variability however poses the main obstacle to gain meaningful effects. We will use our time-wise data to “subtract” measures between time points in the same individual, and analyze our data with repeated measure ANOVA (one factor is time point (intra-subject), other is group (inter-subject)).

Group comparison of the seed based correlation measures is straightforward, correlation values between the vmPFC and other DMN regions and subgenual cingulate will be used to detect any interaction between factors (time and group (responders and non-responders)).

The group analysis of ICA networks will be carried out by dual regression method, as it is presented on Figure 3. Individual network patterns will be obtained, and these individual patterns will be used in a second level analysis with SPM, where voxel based repeated measure ANOVA will be calculated. Similarly individual amplitude maps will be analyzed with SPM.

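### Repeated-measures ANOVA over three scans classically keeps only patients with all three; a mixed model and pairwise difference maps would use every available scan

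*Combined protocol and SAP*

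**What the plan says.** The Rationale promises "longitudinal MRI data (once before ECT and twice after ECT", so each patient has a baseline and two follow-up scans. Section 1 (Study Overview) plans "to recruit 24 patients who are scheduled to receive an acute course of ECT" and adds: "Parallel with these procedures we will also collect magnetic resonance imaging (MRI) data on these subjects".

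The Group analysis section describes subtracting "measures between time points in the same individual, and analyze our data with repeated measure ANOVA", with time point as the within-subject factor and group as the between-subject factor. For seed-based correlations it looks for an "interaction between factors (time and group (responders and non-responders". For the ICA network maps it specifies a voxel-wise repeated-measures ANOVA in SPM, and amplitude maps are handled similarly. The Sample Size and Power section generalises this: "We will use repeated measure ANOVA to analyze each of the neuroimaging measures between different timepoints". That section takes 80% power at N=20 from a cited methods paper and remarks that "targeting for 20 subjects in neuroimaging studies is a common practice".

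No section gives a scan-loss rate, an allowance for loss, or a rule for a patient with one scan missing. Exits are foreseen, however. Section 6 (ECT Procedures) withdraws patients with limiting side effects, the Premature exits list gives four routes out, and section 9 says: "In the case of a serious or intolerable adverse event subjects will be withdrawn from the study".

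Two further passages matter. Section 13 (Data Analysis) uses mixed models with a random subject effect for the HRSD and each cognitive measure. Section 3 (Inclusion/Exclusion Criteria) lets patients who do not qualify for the anesthetic comparison join the imaging part alone, without stating how many are expected.

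**The concern.** Classical repeated-measures ANOVA works on complete sets. With three scans and time as a factor, a patient with scans 1 and 2 but no scan 3 contributes nothing, even to the change from scan 1 to scan 2.

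That loss falls on a question the plan treats as distinct. The background section on neuroimaging in ECT argues that scans soon after ECT and scans some weeks later may show opposite changes. Secondary Aim B likewise separates the change after ECT from its later course. A patient who has the early scan only is fully informative about the early change.

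The loss may also be selective. Patients who leave because of side effects, withdrawn consent or a discontinued course are plausible candidates for missing later scans. The analysed set can then lean towards patients who tolerated and completed ECT. The plan compares responders with non-responders but does not define response for imaging. If it follows the Non-remitter criteria section, which counts premature exits as non-remitters, missing scans would collect in one of the two groups.

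**Working it through.** **The plan's own figure.** N=20 for 80% power cannot be reproduced. The alpha, the sidedness and the standard deviations are not stated, and the figure is borrowed. It is used below only as the plan's benchmark.

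**Inputs.** Starting patients: 24 (section 1). Follow-up scans: 2 (Rationale). Benchmark: 20 (Sample Size and Power). Loss per follow-up scan, q: not in the documents, so it is assumed and varied from 5% to 20%. The baseline scan is assumed present for all.

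**Without any assumption on q.** 24 − 20 = 4. Four patients with any missing scan can be absorbed; a fifth leaves 19.

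**Expected complete sets of three scans.** Independent loss: 24 × (1 − q)². The same patients missing both scans: 24 × (1 − q). Different patients missing each scan: 24 × (1 − 2q).

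| q | Independent | Same patients | Different patients | P(fewer than 20), independent |
|---|---|---|---|---|
| 5% | 21.66 | 22.8 | 21.6 | 0.08 |
| 10% | 19.44 | 21.6 | 19.2 | 0.49 |
| 15% | 17.34 | 20.4 | 16.8 | 0.84 |
| 20% | 15.36 | 19.2 | 14.4 | 0.97 |

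Break-even under independence is 1 − √(20/24) = 8.7% per scan, which is 1 − 20/24 = 16.7% of patients with an incomplete set.

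**What pairwise contrasts recover.** The number of patients with baseline and scan 2 is 24 × (1 − q). For baseline and scan 3 it depends on the pattern of loss:

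- *Intermittent, independent misses:* 24 × (1 − q) for both contrasts, so 21.6 each at 10% against 19.44 complete sets.
- *Permanent dropout at rate q before each follow-up scan:* 24 × (1 − q) for scan 2 but 24 × (1 − q)² for scan 3. At 10% these are 21.6 and 19.44; at 15%, 20.4 and 17.34. The scan-3 pairs equal the complete sets, so only the scan-2 contrast gains.
- *The same patients miss both scans:* pairs equal complete sets (21.6 at 10%), and nothing is gained.

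**Effect on power, for scale only.** Take a one-sample t-test on within-patient differences and solve for the effect that gives 80% power at N=20. For example, this is 0.66 SD at two-sided 5%. Over two-sided alphas of 0.05, 0.01, 0.002 and 0.001 and a one-sided 0.05, power is about 76–78% at N=19 and about 54–68% at N=15.

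**Imaging-only patients.** At 10% independent loss, one extra patient gives 25 × 0.81 = 20.25 expected complete sets, and 28 starters give 28 × 0.81 = 22.68.

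**The case against.** The plan never says that a patient with a missing scan is dropped. A reader might infer such a rule, but it is a property of the classical method, not a stated instruction. The plan also speaks of subtracting time points within a person, and a difference between two scans needs only those two. This stands in part. The differences are still to be analysed by an ANOVA with time as a factor, and over three scans that again needs every time point.

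A reader might also infer that the imaging sample will fall below its target. The documents do not support that. They give no loss rate. At an assumed 10%, the expected shortfall is 20 − 19.44 = 0.56 of a patient, close to an even chance, and costs 2 to 4 points of power at N=19. The 20 is a borrowed benchmark, not a requirement calculated for this three-scan design. The sample is not capped at 24 either, because imaging-only patients may join. Their number is unplanned, however, and they would restore numbers without removing any selection.

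Three other stronger readings also fail:

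- Bias is possible but not shown. Nothing in the documents links scan loss to connectivity change.
- Section 13 specifies mixed models for the HRSD and cognition, not for every non-imaging repeated outcome; seizure and hemodynamic measures have no stated model.
- Uneven spacing of the patients' scans cannot be asserted, since their timeline is in a figure that is not shown; exact intervals are given only for the healthy volunteers.

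Finally, imaging is Secondary Aim B of a pilot, which limits the weight of the point.

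**Conclusion.** The point holds as a choice of analysis. The named method, in its usual form, discards usable scans and removes patients from an early contrast to which they could contribute. The plan already uses a method for the HRSD and cognition that would avoid this.

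The size is modest and uncertain. With 24 starters, the benchmark of 20 is missed once five patients lack any scan. Under independent loss, the expected complete sets run from 21.7 at 5% to 15.4 at 20% per scan, and the result at 10% depends on how far the losses overlap. These figures rest on an assumed loss rate, complete baseline scans and no imaging-only patients.

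It would be too strong to say that pairwise contrasts keep every comparison at 20 or above with 15% loss. That is true only if patients who miss scan 2 return for scan 3. The exits that the plan describes are mostly permanent, and in that case 17.3 pairs are expected for scan 3.

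**What to change.** In the Group analysis and Sample Size and Power sections, replace repeated-measures ANOVA as follows.

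1. **Region-level connectivity.** Use a linear mixed model with scan as a factor, group and scan-by-group, all available scans, and an unstructured within-patient covariance. If it does not converge, use a random intercept with robust or small-sample-corrected standard errors. A random intercept alone would not do, because it implies equal variances and equal correlations across scans and so does not relax the ANOVA's assumption about the variances of differences.
2. **Voxel-wise maps.** Run separate within-patient difference analyses for baseline to scan 2 and baseline to scan 3, each with every patient who has that pair.
3. **Reporting.** Give the number of patients in each contrast.

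The cost is a change of wording and slightly more analysis work; no extra patients or scans are needed. There are three downsides. Two voxel-wise contrasts take the place of one test. The mixed model is valid if scans are missing at random, and the pairwise maps still exclude anyone without that pair, so selective loss is reduced at best. Under permanent dropout, the gain is mainly in the baseline-to-scan-2 contrast.

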Since this is a pilot study, the goal is to estimate the magnitude of the effect sizes for use in designing a subsequent study. With 12 patients randomized to each of the two treatment groups, there is only 45% power with an alpha level of 5% to detect a difference of 50% remission rate in the methohexital group and an 80% remission rate in the ketamine group at visit 8. For the other aims, which look at the change in scores on various rating scales over time, there will be 80% power with an alpha level of 5% (2-sided) to detect a difference between the slopes (measuring rate of change in scores on tests per visit) for the two treatment groups of magnitude  $0.05\sigma$ , where  $\sigma$  is the standard deviation of scores in either treatment group at a single visit. If, for example, the standard deviation of the HRSD scores is 5.0, then there will be power to detect an increased rate of improvement in the ketamine group of 0.25 points per visit, corresponding to an average improvement of 2.0 more points per 8 visits in the ketamine group than whatever improvement is observed in the methohexital group (Diggle et al 1995).

Given the recognition that, with the small sample size, power will be low, the primary focus of analysis is to determine whether ECT with ketamine anesthesia compared to ECT with methohexital anesthesia produces a clinically significant effect, i.e., one that, even if it does not reach statistical significance, would justify a larger clinical trial to replicate effect size. We expect a mean number of 8 treatments to remission based on the results of a Consortium for Research in ECT paper.

Our specific hypothesis is that ECT will decrease functional connectivity in the Default Mode Network (time-wise hypothesis). We also think that the decrease in the expression of this network will correlate with the effectiveness of the ECT, or at least will show a difference

between responders and non-responders (group-wise hypothesis). In order to detect network changes, we will calculate seed based correlation, ICA network expressions and amplitude measures of the networks.

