### **Amplitude measures**

Amplitude of spontaneous low-frequency fluctuations. To examine the potentially meaningful information contained within the ALFF, two fast-Fourier transformation (FFT)-based indices, ALFF and fALFF, will be used to compute the amplitude of low-frequency fluctuations in the frequency domain. For each individual, ALFF and fALFF will be computed to identify those voxels with significantly detectable low-frequency fluctuation amplitudes. Specifically, at each voxel, ALFF is calculated as the sum of amplitudes within a specific low frequency range (0.01-0.1 Hz). fALFF is the normalized ALFF, calculated by dividing the ALFF value by the total sum of amplitudes across the entire frequency range measured in a given time series. Voxelwise ALFF and fALFF maps will be calculated for each participant in native space, and then will be transformed into the MNI152 standard brain space with 3-mm isotropic voxel size. Before statistical analyses, each individual ALFF or fALFF map will be Z-transformed (i.e., by subtracting the mean voxelwise ALFF or fALFF obtained for the individuals entire brain, and then dividing by the corresponding SD) to improve its suitability for group-level parametric analyses. The individual Z-transformed ALFF or fALFF maps will be used in subsequent group- and center-level analyses. Multiple comparisons will be corrected at the cluster level using Gaussian random field theory (min  $Z>2.3$ ; cluster significance:  $p<0.05$ , corrected).

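### The imaging plan's 80% power at N=20 rests on task signal change over time; it covers neither the connectivity measures nor the responder contrast, and two sections disagree on the main imaging goal

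*Combined protocol and SAP*

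**What the plan says.** Sample Size and Power gives the objective of the imaging work as to "examine and validate the differences in neuroimaging changes and network expressions across different time points during the ECT treatment", analysed by repeated-measures ANOVA. It says that for a power calculation "we have to estimate the distribution of the magnitude of signal change and the within subject and between subject variance". It gives a size for the signal ("with cognitive or perception tests the signal is usually around 0.5-1" percent) but none for either variance. It then cites a published fMRI sample-size paper for the statement that "80% power can be reached with" N=20.

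Group analysis, a few lines earlier, says: "Our main goal in our analysis is to determine group-wise effects". For the seed-based analysis, correlation values "will be used to detect any interaction between factors (time and group (responders and non-responders". ICA and amplitude maps go to a voxel-based repeated-measures ANOVA, but the groups for those maps are not named.

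Section 13, Data Analysis, makes a fall in Default Mode Network connectivity over time the specific hypothesis. It adds second that this fall should correlate with ECT effectiveness or at least differ "between responders and non-responders (group-wise hypothesis"). Secondary Aim B, item (c), looks for networks correlated with better clinical outcome. Section 7.d defines remitters and non-remitters; responder is not defined.

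**The concern.** The only imaging power figure differs from the group-wise analysis in two ways.

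- **Measure.** Percent signal change in a task is not a correlation coefficient, an ICA map weight or a low-frequency amplitude. A sample size for the first says nothing direct about the others.
- **Design.** A within-patient change uses every patient in one comparison. A responder contrast divides the same patients into two groups, probably of unequal size, and compares their changes.

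A reader who takes 80% at N=20 as covering the imaging aims would overrate what the responder contrast can show, and could give a null result there more weight than it can bear.

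**Working it through.** **1. The plan's own figure.** It cannot be reproduced. The section gives no alpha, sidedness, test or SD, and does not say whether 20 is a total or a group size. The missing SD alone decides the answer: for a 0.5% change in a paired t test at N=20 and two-sided 0.05, power is 98.9% if the SD of the change is 0.5, 80.7% at 0.75, 56.5% at 1.0 and 29.4% at 1.5.

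**2. Standardized effect implied by 80% at N=20.** Assume a one-sample (paired-change) t test at two-sided 0.05. The noncentrality is d × √20. Solving the noncentral t for 80% power gives d = 0.66. The normal approximation gives (1.960 + 0.842)/√20 = 0.63. For the time-wise contrast this effect has 80% power at N=20 by construction, and 87% at N=24.

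**3. The same d as a between-group difference in change scores.** Two-sample t test, two-sided 0.05, noncentrality d × √(n1·n2/(n1+n2)). For 12 v 12 this is 0.66 × √6 = 1.62; for 16 v 4 it is 0.66 × √3.2 = 1.18. The plan recruits 24 randomized patients and cites 20 for imaging. The responder share is not given. I used 50% to 85%; the Rationale's general figure for ECT efficacy is 65 to 85%.

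| Split | Total | Power at d = 0.66 | d for 80% power |
|---|---|---|---|
| 12 v 12 | 24 | 34% | 1.20 |
| 16 v 8 | 24 | 31% | 1.27 |
| 20 v 4 | 24 | 21% | – |
| 10 v 10 | 20 | 29% | 1.32 |
| 13 v 7 | 20 | 27% | 1.39 |
| 16 v 4 | 20 | 20% | 1.66 |
| 17 v 3 | 20 | 17% | – |

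For 80% power at d = 0.66 the contrast would need about 74 patients in an even split, 82 at 65% responders and 144 at 85%.

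**4. Sensitivity to alpha.** For splits from 16 v 4 to 12 v 12:

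- one-sided 0.05 in both steps: 26-39%
- two-sided 0.01 in both steps: 11-25%
- two-sided 0.001 in both steps: 5-17%
- effect implied at 0.001 but contrast tested at 0.05: 45-71%

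With one alpha for both steps, power at N = 20-24 does not exceed about 39%.

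**5. Sensitivity to N.** Section 3 admits imaging-only patients, number unstated. If they raised the total to 40, power at d = 0.66 would be 53% (20 v 20) or 49% (26 v 14).

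**6. A continuous outcome instead of a split.** Fisher z at N=24: (1.960 + 0.842)/√21 = 0.611, so the detectable correlation is tanh(0.611) = 0.545. For the split, the point-biserial r is d/√(d² + 1/(pq)), where p and q are the two group shares:

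- 12 v 12: 1.197/√(1.432 + 4) = 0.513
- 16 v 8: 1.269/√(1.611 + 4.5) = 0.513

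Under bivariate normality, dichotomizing shrinks r by 0.798 (even split) or 0.771 (2:1). The underlying r needed is therefore 0.513/0.798 = 0.64 or 0.513/0.771 = 0.67.

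Steps 2 to 6 include no voxel-wise or cluster correction. The plan's stated threshold for the amplitude maps is "cluster significance: $p<0.05$ , corrected".

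**The case against.** The best defence is that the 80% figure sits beside a time-wise objective and matches it in design. The Hypothesis section and section 13 also put the time-wise fall in connectivity first and the responder difference second. That stands: a reader might infer that the imaging study is powered at a third or less for its agreed main goal, but the documents do not agree on a main goal. What remains is the conflict with Group analysis. Even for the time-wise test, the figure concerns task signal and not connectivity.

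A reader might also infer that the 80% is a miscalculation. The documents do not show that: the inputs needed to check it are absent, and the cited paper was not available here.

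The illustrative power depends on carrying a d over from a measure that does not apply to correlations. That is fair, and is why it can serve only as a yardstick for the effect of splitting the sample. The responder split is named only for the seed-based analysis. For the ICA and amplitude maps the groups could equally be patients and the healthy controls, who are also scanned three times. Three scans in a repeated-measures ANOVA may give different power from a single change score.

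The study is a pilot, and section 13 openly concedes low power for remission. The imaging section calls power analysis challenging but makes no such concession for the responder contrast. Nor do the documents set a rule by which a null responder contrast would refute the network hypothesis, so misreading is a risk and not a planned inference.

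**Conclusion.** The point holds as one of scope and consistency. Sample Size and Power and Group analysis name different main goals, and the 80% at N=20 is established neither for connectivity measures nor for the responder contrast. Seeing this needs no assumption.

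The size is conditional. It assumes a paired test at two-sided 0.05 behind the 80%, an equal standardized effect for the group difference in change scores, one change score per patient, no imaging dropout and no multiplicity correction. On those terms power is about 17-34% with 20-24 patients (17 v 3 to 12 v 12), and about 49-53% if the total reached 40. Only a stricter alpha behind the 80% than for the contrast itself lifts it well above the 39% ceiling at N = 20-24. The detectable d needs fewer assumptions, since it does not use the 0.66: about 1.2 (12 v 12) to 1.7 (16 v 4), a very large difference.

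**What to change.** - **Reconcile the goal.** Make Group analysis and Sample Size and Power name the same main imaging goal.
- **Limit the 80% figure.** State that it applies at most to within-patient change in task signal and is not established for seed-based, ICA or amplitude measures.
- **Describe the responder contrast.** Give its detectable difference (d about 1.2 to 1.7 for the splits above) with the assumed alpha, split and N, before correction, and label it exploratory. Name the groups for the ICA and amplitude maps.
- **Use a continuous outcome.** In Group analysis, replace the undefined responder split with percent change in HRSD as the between-subject term. This fits Secondary Aim B (c) and the correlation already intended in section 13. Under bivariate normality at N=24 it detects r of about 0.55 with 80% power, against an underlying r of about 0.64-0.67 after dichotomizing. The plan does not say which ratings imaging-only patients receive, so their HRSD before and after ECT should be confirmed.

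The cost is SAP wording and a less favourable stated power. No more patients are needed.
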